5.1. TVB-2640

The clinical safety profile to date for TVB-2640 is based primarily on one completed uncontrolled open-label Phase 1 study in humans (Study 3V2640-CLIN-002) in 136 patients with solid tumors, 76 treated with monotherapy (at doses ranging from 60 mg/m² to a dose of 240 mg/m² (i.e., up to 600 mg) and 60 treated with TVB-2640 in combination with a taxane (paclitaxel or docetaxel).

Overall, TVB-2640 demonstrated a favorable tolerability profile. Most treatment-emergent adverse events (TEAEs) were Grade 1 or 2 in intensity, non-serious, and manageable.

As anticipated, based on nonclinical study findings, the principal toxicities associated with TVB-2640 as monotherapy were skin and ocular effects. With monotherapy, most skin events were Grade 1 or 2 in intensity, and all were non-serious.

The maximum tolerated dose (MTD) of TVB-2640 monotherapy in patients with solid tumors was determined to be 100 mg/m². Dose-limiting toxicities (DLTs) associated with TVB-2640 monotherapy were skin and ocular events, including corneal edema, keratitis, and palmar-plantar erythrodysesthesia (PPE) syndrome.

As monotherapy, the most common individual TEAEs were alopecia (61%), PPE syndrome (46%), fatigue (37%), decreased appetite (26%), and dry skin (22%).

When TVB-2640 was administered in combination with a taxane (paclitaxel or docetaxel), skin and ocular effects also were common. Most skin events were Grade 1 or 2 in intensity, and all but 1 skin event were non-serious.

As was the case with monotherapy, the MTD of TVB-2640 in combination with paclitaxel was determined to be 100 mg/m². DLTs associated with TVB-2640 in combination included PPE syndrome and uveitis. The most common TEAEs with TVB-2640 in combination with paclitaxel were fatigue (53%), alopecia (46%), PPE syndrome (46%), nausea (40%), and peripheral neuropathy (36%). Peripheral neuropathy is known to be associated with paclitaxel.

When TVB-2640 was administered in combination with paclitaxel, 6 episodes of serious pneumonitis were experienced by 5 patients, with all assessed by the Investigator as related to both TVB-2640 and paclitaxel. (No cases of pneumonitis were reported among monotherapy patients.) Given the occurrence of these events, respiratory events were identified as adverse events of special interest for patients receiving TVB-2640 in combination.

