8.6. Subject Withdrawal Criteria

Subjects will be informed that they have the right to withdraw from the study at any time for any reason, without prejudice to their medical care. Study drug must be permanently discontinued

and the subject withdrawn from the study for any of the following TEAEs, with the subject managed as indicated:

- **Palmar-plantar Erythrodysesthesia (PPE):** For mild to moderate symptoms of PPE (e.g., redness, pain, or scaling of hands or feet), study drug should be interrupted and symptomatic measures, including hand cream such as “Udder Cream”, instituted immediately. Study drug may be resumed after resolution of symptoms. Study drug should be permanently discontinued at the first sign of significant/severe, redness, pain, or scaling of hands or feet, and symptomatic measures instituted immediately.
- **Dyspnea or suspected pneumonitis:** Study drug should be permanently discontinued for subjects with shortness of breath or other respiratory symptoms that are otherwise unexplained. The subject is to be carefully monitored for improvement. In the event that symptoms worsen or present as more than mild intensity, immediate referral to a qualified pulmonologist for definitive diagnosis and treatment should be undertaken.
- **Visual symptoms (including keratitis):** Study drug should be permanently discontinued at the first sign of significant, redness, pain, or dryness of the eyes. Symptomatic measures, including moisturizing eye drops should be instituted. In the event that symptoms worsen or present as more than mild, immediate referral to a qualified ophthalmologist should be undertaken.
- **Evidence of drug-induced liver injury (DILI);** Study drug should be permanently discontinued for subjects with evidence of DILI; see [Appendix A](#) for details.

Refer to the Study Manual for additional details regarding the assessment and management of these events.

Furthermore, the Investigator also has the right to withdraw subjects from the study for any of the following reasons:

- Progression of underlying disease that, in the opinion of the Investigator, precludes further study treatment.
- Occurrence of any other unacceptable AE.
- Study drug interruption for any reason for >7 days.
- Subject requires use of a prohibited concomitant medication or therapy.
- General or specific changes in the subject’s condition unacceptable for further treatment within the study parameters, in the judgment of the Investigator.
- Non-compliance.

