9.6. Dose Reductions

Dose reductions for the management of other study drug-related toxicities are permissible for subjects assigned to TVB-2640 50 mg or 75 mg with the approval of the Medical Monitor.

- Subjects assigned to 50 mg may have the dose reduced to 25 mg. In such cases, subjects will receive 1 25-mg tablet.
- Subjects assigned to 75 mg may have the dose reduced to 50 mg. In such cases, subjects will receive 1 50-mg tablet.

Subjects for whom the study drug dose is reduced are to continue treatment at the reduced dose for the remainder of the treatment period. At the time the dose is reduced, all study drug is to be returned and study drug will be redispensed according to the reduced dose.

Subjects receiving 25 mg for whom a dose reduction is deemed necessary should be discontinued from the study.

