8.2. Study Drug Exposure and Compliance

Duration of drug exposure will be summarized both as a continuous and a categorical variable for the safety population. Exposure will be calculated as:

$$\text{study drug stop date} - \text{study drug start date} + 1 \text{ [converted to weeks (days divided by 7)]}$$

Categories for reporting exposure will include < 2 weeks; 2 weeks - <4 weeks; 4 weeks - <8 weeks; 8 weeks - <12 weeks; \geq 12 weeks.

Drug accountability is captured in the eCRF at each visit. The eCRF captures the number of pills dispensed, the number returned, and the number missed during the dosing period. Overall compliance will be determined based on pill counts over each visit period and taking into account the number missed. Compliance will be derived as:

$$\frac{[(\text{# of pills dispensed} - \text{# of pills returned}) - \text{# of missed pills}]}{\text{number of days within the visit period}} \times 100$$

Where number of days within the visit period is derived as:

$$\text{Date of Visit (X+1)} - \text{Date of Visit (X)} + 1$$

Compliance will also be summarized for the following categories < 80%, 80% - 120%, and > 120%.

Mean daily dose (mg) and total cumulative dose (mg) received will also be summarized. Total cumulative dose will be summarized overall and separately for those that had extended dosing.

Listings of planned and actual treatments, overall compliance, and drug exposure will be produced.

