Sponsor: Sagimet Biosciences

Protocol Number: 3V2640-CLIN-005

Version and Date: Final Version 1, 02June2020

An overview of TEAEs will be produced, including counts and percentages of subjects with any incidences of: TEAEs, TEAEs related to study treatment, serious adverse events (SAEs), TEAEs leading to study drug discontinuation, SAEs, and fatal SAEs. The number of AEs will also be included on the summary.

In addition to the overview of TEAEs, the following summaries of AEs will be provided for the safety population by treatment group and overall:

- TEAEs by SOC and PT
- TEAEs related to study treatment by SOC and PT
- CTCAE Grade 3 or higher TEAEs by SOC and PT
- CTCAE Grade 3 or higher TEAEs related to study treatment by SOC and PT
- TEAEs leading to treatment discontinuation by SOC and PT

Summaries of TEAEs by SOC, PT, and maximum severity as well as TEAEs by SOC, PT, and maximum relationship to study treatment will also be prepared.

A comprehensive listing of all AEs will be provided in a by-subject data listing. AEs that began after 84 days of dosing will be identified on the listing. In addition, the following listings will be provided:

- TEAEs related to study treatment
- SAEs
- TEAEs leading to treatment discontinuation; and
- Fatal AEs.

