APPENDIX 2. PLANNED TABLES, LISTINGS, AND FIGURES

Sponsor: Sagimet Biosciences

Protocol Number: 3V2640-CLIN-005

Version and Date: Final Addendum 1, 14Mar2022

Type	Number	Title	Population
Table	14.1.1	Summary of Subject Disposition	All Subjects
Table	14.1.2.1	Summary of Subject Demographics	Modified Intent-to-Treat Population
Table	14.1.2.2	Summary of Subject Demographics	Safety Population
Table	14.1.3.1	Summary of Subject Baseline Characteristics	Modified Intent-to-Treat Population
Table	14.1.3.3	Summary of Subject Baseline Characteristics	Safety Population
Table	14.1.4.1	Summary of NASH History	Modified Intent-to-Treat Population
Table	14.1.4.3	Summary of NASH History	Safety Population
Table	14.1.5	Summary of Protocol Deviations	Intent-to-Treat Population
Table	14.1.6	Summary of Concomitant Medications	Safety Population
Table	14.1.7	Summary of Study Drug Exposure and Compliance	Safety Population
Table	14.2.1.1.1	Summary of Liver Fat (%) Based on MRI-PDFF	Modified Intent-to-Treat Population
Table	14.2.1.7	Summary of Liver Fat (%) Based on MRI-PDFF Log Ratio Versus Baseline	Modified Intent-to-Treat Population
Table	14.2.2.1.1	Summary of Liver Fat (%) Based on MRI-PDFF - Responder Analysis	Modified Intent-to-Treat Population
Table	14.2.3.1.1	Summary of Liver Aminotransferase Results and Change from Baseline	As-Treated Population
Table	14.2.3.4	Summary of Percentage of ALT and AST Normalization by Visit: Missing Data Excluded	As-Treated Population
Table	14.2.4.1.1	Summary of Lipid and Lipoprotein Results and Change from Baseline	As-Treated Population
Table	14.2.7	Summary of Liver Fibrosis Results as Determined by VCTE	As-Treated Population
Table	14.2.8.1.1	Summary of Metabolic Parameter Results and Change from Baseline	As-Treated Population
Table	14.2.9	Summary of Anthropometric Body Measurement Parameter Results and Change from Baseline	As-Treated Population
Table	14.3.1	Overall Summary of Adverse Events	Safety Population
Table	14.3.2	Summary of Treatment Emergent Adverse Events by SOC and PT	Safety Population
Table	14.3.3	Summary of Treatment Related Treatment Emergent Adverse Events by SOC and PT	Safety Population
Table	14.3.5	Summary of Treatment Emergent Adverse Events Leading to Treatment Discontinuation of Study Treatment by SOC and PT	Safety Population
Table	14.3.7	Summary of Treatment Emergent Adverse Events by SOC, PT, and CTCAE Grade	Safety Population

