Table	14.3.8	Summary of Treatment Related Treatment Emergent Adverse Events by SOC, PT, and CTCAE Grade	Safety Population
Table	14.3.9	Summary of Treatment Emergent Adverse Events by SOC, PT, and Relationship to Treatment	Safety Population
Table	14.3.10	Summary of Selected Clinical Laboratory Results and Changes from Baseline	Safety Population
Table	14.3.14	Summary of Clinical Chemistry Shifts from Baseline	Safety Population
Table	14.3.18	Summary of Vital Signs Results and Changes from Baseline	Safety Population

Sponsor: Sagimet Biosciences

Protocol Number: 3V2640-CLIN-005

Version and Date: Final Addendum 1, 14Mar2022

Type	Number	Title	Population
Table	14.3.19	Summary of ECG Results and Changes from Baseline	Safety Population
Table	14.3.20	Summary of Clinically Significant Ophthalmologic Examination Abnormalities	Safety Population
Listing	16.2.1.1	Patient Disposition	All Subjects
Listing	16.2.1.2	Informed Consent and Randomization	All Subjects
Listing	16.2.2	Protocol Deviations	All Subjects
Listing	16.2.4.1	Demographics	All Subjects
Listing	16.2.4.2	Social History	All Subjects
Listing	16.2.4.3	Baseline Internal Laboratory Results	All Subjects
Listing	16.2.4.4	Medical History	All Subjects
Listing	16.2.4.5	NASH Confirmation Results	All Subjects
Listing	16.2.4.6	Physical Examination Results	All Subjects
Listing	16.2.4.7	Prior and Concomitant Medications	All Subjects
Listing	16.2.5.1	Study Drug Accountability	All Subjects
Listing	16.2.5.2	Study Drug Administration	All Subjects
Listing	16.2.5.3	Study Drug Dosing Adjustments	All Subjects
Listing	16.2.6.1	MRI-PDFF Results	All Subjects
Listing	16.2.6.2	Lipid and Lipoprotein Parameter Results	All Subjects
Listing	16.2.7.1	All Adverse Events	All Subjects
Listing	16.2.7.2	Treatment Related Treatment Emergent Adverse Events	All Subjects
Listing	16.2.7.3	Serious Adverse Events	All Subjects
Listing	16.2.7.4	Treatment Emergent Adverse Events Leading to Treatment Discontinuation	All Subjects
Listing	16.2.7.5	Treatment Emergent Adverse Events of Special Interest	All Subjects
Listing	16.2.7.6	Fatal Adverse Events	All Subjects
Listing	16.2.8	Selected Laboratory Results	All Subjects
Listing	16.2.8.1	Clinical Chemistry Results	All Subjects
Listing	16.2.8.2	Hematology Results	All Subjects
Listing	16.2.8.3	Coagulation and Urinalysis Results	All Subjects
Listing	16.2.8.4	Other Laboratory Results	All Subjects
Listing	16.2.8.5	Vital Signs	All Subjects
Listing	16.2.8.6	ECG Results	All Subjects

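### Discontinuation is the only action taken that SAP 8.5.1 tabulates, yet protocol 9.6 makes 25 mg subjects stop where 50 mg subjects may be reduced, so the table can understate dose-limiting toxicity at 50 mg

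*SAP*

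**What the plan says.** **Rules for stopping and reducing.** Protocol 8.6 requires study drug to be stopped "and the subject withdrawn from the study for any of the following TEAEs": severe palmar-plantar erythrodysesthesia (PPE), otherwise unexplained dyspnea or suspected pneumonitis, significant eye signs, and drug-induced liver injury. These rules do not differ by dose. Protocol 9.6 covers the rest. Reductions for "other study drug-related toxicities are permissible for subjects assigned to TVB-2640 50 mg or 75 mg with the approval of the Medical Monitor". A 50 mg subject goes down to 25 mg and continues on that dose to the end of treatment. At the lowest dose there is no lower step: "Subjects receiving 25 mg for whom a dose reduction is deemed necessary should be discontinued from the study".

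**Reporting.** SAP 8.5.1 plans by-arm summaries of all, related, Grade 3 or higher, and related Grade 3 or higher TEAEs, and of TEAEs by maximum severity and by maximum relationship. By action taken it names discontinuation only: a row in the overview, a table of "TEAEs leading to treatment discontinuation by SOC and PT", and a listing. It names no summary of events leading to reduction or interruption. Protocol 12.2.3 has the investigator record the action taken for every AE.

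**Related outputs.** SAP 8.2 states: "Mean daily dose (mg) and total cumulative dose (mg) received will also be summarized". SAP section 7 puts all data into by-subject listings, and 8.5.1 adds a comprehensive AE listing. The Cohort 3 output list in Addendum 1 has a "Study Drug Dosing Adjustments" listing, and its one AE table by action taken is the "Summary of Treatment Emergent Adverse Events Leading to Treatment Discontinuation of Study Treatment by SOC and PT".

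**The concern.** A discontinuation table by arm invites the reader to compare tolerability at 25 mg and 50 mg. Under protocol 9.6 the same toxicity, judged to need the same response (a lower dose), counts in that table at 25 mg but need not count at 50 mg. Part of any difference between the two columns is then produced by the dosing rule, and its direction is known: it makes 50 mg look better than it is relative to 25 mg.

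This bears on a stated aim. Protocol 9.7 says the AE profile of the doses will feed into dose optimisation for later studies, and safety is one of the two primary objectives. Mean daily dose would show that reductions happened, but not which events led to them.

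**Working it through.** The plan gives no figure to reproduce here and no rate for any of these events. The first two steps compare the texts; the others are illustration with assumed rates.

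**1. Is the affected class empty?** Protocol 5.1 lists the five most common monotherapy TEAEs in the oncology study: alopecia 61%, PPE 46%, fatigue 37%, decreased appetite 26%, dry skin 22%. Of these, only PPE is named in protocol 8.6. The other four fall under 9.6 if they need a dose change. This shows which kinds of event are plausible, not how often they will occur at 25 or 50 mg.

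**2. Does another named summary fill the gap?** The incidence and severity tables count an event whatever was done about it, so the dosing rule does not directly affect them; but they do not show which events limited dosing. Mean daily and cumulative dose are not linked to events. The listings hold the link subject by subject, untabulated.

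**3. Model.** Let p be the proportion with a toxicity outside 8.6 that calls for a lower dose, s the proportion stopped under 8.6, and q the share of the p group at 50 mg who are reduced and kept on drug. Each subject is counted once.

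- Discontinuation at 25 mg: D25 = s25 + p25
- Discontinuation at 50 mg: D50 = s50 + p50(1 − q)
- D50 ≤ D25 when q ≥ 1 − (p25 + s25 − s50)/p50

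With equal s, the threshold is 1 − p25/p50: 33%, 50% and 67% when p50 is 1.5, 2 and 3 times p25. With s of 3% at 25 mg and 6% at 50 mg:

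- p 10% vs 20%: 1 − (0.10 − 0.03)/0.20 = 65%
- p 5% vs 10%: 1 − (0.05 − 0.03)/0.10 = 80%
- p 3% vs 6%: 1 − (0.03 − 0.03)/0.06 = 100%
- p 2% vs 4%: 1 − (0.02 − 0.03)/0.04 = 125%, which cannot be reached

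**4. What the table would show.** Take s of 3% and 6% and 30 subjects per arm (the planned US number on each active dose). The chance that the observed 50 mg count is no higher than the 25 mg count is the sum over k of P(X25 = k) × P(X50 ≤ k), with independent binomial counts.

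| p at 25 / 50 mg | D25 | D50 at q = 0, 50%, 75% | Chance 50 mg count ≤ 25 mg count |
|---|---|---|---|
| 10% / 20% | 13% | 26%, 16%, 11% | 0.129, 0.442, 0.671 |
| 2% / 4% | 5% | 10%, 8%, 7% | 0.31, 0.42, 0.48 |

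In the first row, discontinuation or reduction combined is 13% vs 26% whatever q is: 30 × 0.13 = 3.9 and 30 × 0.26 = 7.8 expected subjects. In the second row the true order never reverses, and small counts already give a 31% chance of 50 mg looking no worse with no reductions at all.

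**The case against.** **Nothing is lost.** The by-subject listings, the comprehensive AE listing and the recorded action taken allow each reduction to be traced to its event, and with 30 to 48 planned active subjects per dose that is feasible. This stands: what is missing is a tabulation, not information.

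**No planned inference depends on it.** Discontinuation is not among the safety endpoints in protocol 6.4.2 or SAP 4.2, and no formal safety testing is planned. This stands too. A reader might infer that the whole AE comparison between doses is biased; the documents do not support that, because the incidence, relatedness, Grade 3 or higher and severity tables do not depend on what was done with the dose.

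**The record is incomplete.** The main SAP's own output list is not in the text available; the list that can be read belongs to Addendum 1 and covers Cohort 3. That list contains outputs which 8.5.1 does not name, such as related TEAEs by grade. One therefore cannot say that no reduction table is planned anywhere, only that 8.5.1 names none.

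**The example may be too high.** The oncology rates come from cancer patients at 60 to 240 mg/m². Closer evidence points lower: in the 10-day metabolic-syndrome study, none of the 6 men on 50 mg had a TEAE, and across 50 to 150 mg all TEAEs were Grade 1 with none leading to discontinuation. The sample is small and exposure short, but it is a fair reason to give the low-rate row equal weight.

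**A combined count has its own lean.** Reducing is an easier decision than stopping, and site staff other than imaging personnel are unblinded. Counting reductions with discontinuations may therefore overstate toxicity at 50 mg. This is why the combined count should stand beside discontinuation and not replace it.

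**Conclusion.** The point holds in a limited form. For toxicities outside protocol 8.6, the discontinuation row and SOC/PT table in SAP 8.5.1 are not comparable between 25 mg and 50 mg, and the rule-driven distortion runs in favour of 50 mg. Its size cannot be known from the documents: it is zero if no 50 mg subject is reduced, large enough to reverse the true order under the higher assumed rates once about two thirds are reduced (threshold 65%), and unable to reverse it under the lowest rates tried. All values of p, s and q are assumptions.

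The consequence is confined to the descriptive comparison of tolerability. A reader might go further and infer that the trial will present 50 mg as the better tolerated dose. The documents do not support that, since reduction is optional, needs Medical Monitor approval, and may never be used. Nor does the argument reach interruptions, whose rules do not differ by dose, or Cohort 3, which is displayed in a single column with no dose beside it for comparison and already has a dosing-adjustment listing. This is a cheap improvement to the plan, not a threat to its main conclusions.

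**What to change.** In the SAP 8.5.1 overview, and in one SOC/PT table for Cohorts 1 and 2, add by arm:

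- TEAEs leading to dose reduction;
- TEAEs leading to discontinuation or dose reduction.

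Derive both from the recorded action-taken field. Show them beside the discontinuation summary whenever 25 mg is compared with 50 mg, with a note that protocol 9.6 offers reduction at 50 mg but not at 25 mg, and that the combined count may lean against 50 mg.

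The cost is two overview rows and one descriptive table, with no new data. Interruption rows and additional Cohort 3 tables are optional; this argument does not require them.

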8.5.2. Clinical Laboratory Evaluations

Clinical chemistry, hematology, coagulation, and urinalysis parameters will be reported based on conventional units as applicable. The following laboratory evaluations will be reported in data summaries:

- Chemistry: Chloride, Carbon dioxide, Sodium, Potassium, Blood urea nitrogen, Calcium, Creatinine, Magnesium, Albumin, Glucose, Total protein, Alkaline phosphatase, AST, ALT, Indirect and direct bilirubin, Creatine phosphokinase (total and fractionated) (screening and baseline only). Note that AST and ALT collected as part of the clinical chemistry panel are also applicable for efficacy assessments.
- Hematology: Hematocrit, Hemoglobin, Red blood cell count, Platelet count, White blood cell count with differential, Absolute neutrophil count.
- Coagulation Studies: Prothrombin time, Activated partial thromboplastin time, international normalized ratio (INR).
- Urinalysis: Specific gravity, Protein, pH, Ketones, Blood, Microscopic examination of sediment, Glucose.

Observed values and changes from baseline for laboratory evaluations will be summarized at each visit and will include the most extreme change from baseline. The percent change from

Sponsor: Sagimet Biosciences

Protocol Number: 3V2640-CLIN-005

Version and Date: Final Version 1, 02June2020

baseline at each visit and the most extreme percent change from baseline will also be summarized. 95% confidence intervals for the change and percent change will be included.

Laboratory data will also be summarized in shift tables of baseline to each visit and most extreme change based on range categories of low (below lower limit of normal [LLN], normal, and high [above upper limit of normal [ULN]]). Urinalysis results and shifts will be based on the categories present in the data.

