2. STUDY OBJECTIVES AND ENDPOINTS

2.1. Primary

The primary objectives of the study are:

- To determine the effect of once daily (QD) TVB-2640 for 12 weeks versus placebo on the change in hepatic fat fraction by proton density fat fraction by magnetic resonance imaging (MRI-PDFF) from baseline in subjects with NASH.
- To determine the safety of QD TVB-2640 versus placebo in subjects with NASH, including the effects on alanine aminotransferase (ALT) and aspartate aminotransferase (AST).

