Similar responder analyses will be performed using response level definitions of 20%, 40%, and 50%. As done for the key secondary endpoint efficacy endpoint, subjects with a reduction of at least 19.5%, 39.5%, and 49.5% from baseline, respectively, will count as responders. Analyses will be repeated in the ITT, ATP, and PP populations. Analyses of the key secondary endpoint performed in the ATP populations will include summaries of all subjects in the analysis population, as well as the subset of subjects that have at least 8 weeks of treatment and an evaluable assessment on/after 8 weeks (i.e., the same subjects in the mITT population).

Similar responder analyses will be performed using reduction in liver fat at End of Study in the mITT, ITT, and ATP populations.

A scatter plot of End of Treatment body weight changes versus End of Treatment liver fat changes will be graphed by treatment and overall in the ATP. A subset will also be run in subjects with at least a 30% reduction in liver fat at Week 12.

In the key secondary analysis, missing Week 12 values for MRI-PDFF will be imputed with the last post-baseline observation on or after Week 8 in the mITT population. Sensitivity analyses excluding subjects with missing data will also be performed.

Other Efficacy Endpoints

Other efficacy endpoints will be summarized using the ATP. A limited set of endpoints will be repeated in the ITT.

Liver aminotransferases will be evaluated using observed values and changes from baseline by study visit. Summaries will be performed for ALT and AST and will be presented by treatment group.

The changes at 12 weeks will be summarized for each treatment group and compared between each TVB-2640 dose group and pooled placebo using a linear mixed-effects model for repeated measures (MMRM). The model will include the stratification factor (diabetes presence/absence),

Sponsor: Sagimet Biosciences

Protocol Number: 3V2640-CLIN-005

Version and Date: Final Version 1, 02June2020

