8.5. Safety

Safety will be evaluated based on data collected for adverse events, vital signs, physical examinations, electrocardiogram (ECG), ophthalmologic examinations, and laboratory data. No

Sponsor: Sagimet Biosciences
Protocol Number: 3V2640-CLIN-005
Version and Date: Final Version 1, 02June2020

formal statistical testing will be conducted for the safety analyses. Descriptive statistics will be used to evaluate safety data in this study. Summaries will be presented by treatment group.

Subset analyses will be performed on all safety endpoints for subjects enrolled in China to evaluate the consistency of results between subjects enrolled in each country.

All safety analysis reporting will be based on the Safety Analysis Set. All safety data will be listed by treatment group and subject.

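### Apart from parameters also analysed as efficacy, the laboratory safety analysis puts 95% intervals only on within-arm change and gives no estimate against placebo

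*SAP*

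**What the plan says.** The second primary objective (SAP 2.1; Protocol 6.1) is comparative: "To determine the safety of QD TVB-2640 versus placebo in subjects with NASH". It names ALT and AST as included effects. Change from baseline in laboratory results is a listed safety endpoint (SAP 4.2).

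SAP 8.5 sets the approach for all safety data: "Descriptive statistics will be used to evaluate safety data in this study", and "Summaries will be presented by treatment group". It adds that no "formal statistical testing will be conducted for the safety analyses". SAP 7.5 defines change as the post-baseline value minus the baseline value. SAP 8.5.2 then summarises each laboratory parameter by visit, with the most extreme change from baseline and shift tables, and states that "95% confidence intervals for the change and percent change will be included". SAP 8.5 and 8.6 mention no dose-minus-placebo difference.

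The transaminases are treated differently. SAP 8.5.2 says: "Note that AST and ALT collected as part of the clinical chemistry panel are also applicable for efficacy assessments". SAP 8.3.2 provides that analysis: "The changes at 12 weeks will be summarized for each treatment group and compared between each TVB-2640 dose group and pooled placebo". It uses a repeated-measures model that reports the pairwise least-squares mean difference, its 95% interval and a p-value at each visit, and it adds stratified comparisons of ALT and AST normalisation.

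**The concern.** The objective asks how the drug compares with placebo. For most of the laboratory panel, the only planned interval asks whether an arm changed from its own baseline. Within an arm, the expected change is the drug effect plus whatever moves all arms alike: regression to the mean after eligibility screening, changes in diet or alcohol use, season, or assay drift. Placebo is there to remove that second part, but in SAP 8.5.2 it appears only as another column with its own before-and-after interval.

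An interval on drug that excludes zero, beside one on placebo that includes it, is easily read as a signal. The reverse pattern is easily read as reassurance. Neither comparison measures the difference between arms or its uncertainty. The affected parameters matter here: the protocol's Appendix A bases interruption and discontinuation decisions partly on bilirubin, ALP and INR, and the Safety Review Committee reviews bilirubin elevations (Protocol 8.7).

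**Working it through.** **1. The plan's own safety figure.** The only numerical safety statement (Protocol 13.1, SAP 3.3) is a chance of at least 95% of seeing at least one adverse event in an arm of 30 at a true rate of 10%. Exact value: 1 − 0.9^30 = 1 − 0.0424 = 0.958. It reproduces, but it describes a single arm and says nothing about precision against placebo.

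**2. Which laboratory and related parameters get a placebo comparison.**

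| Parameter | Comparison with pooled placebo | Where |
|---|---|---|
| ALT, AST | Model difference with 95% interval at each visit; normalisation comparison | SAP 8.3.2 |
| Lipids and lipoproteins | Same model | SAP 8.3.2 |
| Metabolic panel, including glucose and GGT; blood pressure | Analysed in a similar way | SAP 8.3.3, 8.6.1 |
| Direct and indirect bilirubin, ALP, albumin, total protein, creatinine, BUN, electrolytes, calcium, magnesium | None stated | SAP 8.5.2 |
| Haemoglobin, haematocrit, red and white cells, neutrophils, platelets | None stated | SAP 8.5.2 |
| PT, INR, aPTT | None stated | SAP 8.5.2 |

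**3. Width of the missing interval.** Units are the SD of the change score, because the documents give no laboratory SD. These are unadjusted t intervals.

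- Within one arm of 30: t(29)/√30 = 2.045/5.477 = 0.37 SD.
- Between arms, 30 v 30: t(58) × √(1/30 + 1/30) = 2.002 × 0.258 = 0.52 SD.
- With China, 48 v 39: 1.988 × 0.216 = 0.43 SD.
- 25 mg cohort alone, 30 v 15: 2.017 × 0.316 = 0.64 SD.

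Baseline adjustment would usually narrow the between-arm values somewhat.

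**4. What the within-arm interval responds to (illustration).** Assume no drug effect, n = 30, and a shared change of c SD. The within-arm interval excludes zero with the two-sided 5% noncentral-t probability on 29 df, with noncentrality c√30.

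| Assumed shared change c | Noncentrality | Within-arm interval excludes zero | Between-arm interval excludes zero |
|---|---|---|---|
| 0.2 | 1.10 | 18.5% | 5% |
| 0.3 | 1.64 | 35.5% | 5% |
| 0.5 | 2.74 | 75.4% | 5% |

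**5. The most extreme change.** SAP 8.5.2 does not define its direction, and the sentence on intervals does not say whether it covers it. I simulated 20,000 trials with n = 30, five post-baseline visits, no drug effect and between-visit correlation 0.5 to 0.9. If the term means the largest rise, the within-arm interval excludes zero in about 99.9% of trials. If it means the change of largest magnitude with its sign kept, it does so in about 5%. The meaning of the interval therefore depends on a definition that the SAP does not give.

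**The case against.** The strongest objection is that the objective names only ALT and AST, and both get exactly the comparison asked for. The model runs in the as-treated population, which has the same membership rule as the safety population (SAP 5). A reader might infer from SAP 8.5.2 that safety versus placebo is never estimated between arms. The documents do not support that. Two limits remain: the objective includes ALT and AST without being confined to them, and the SAP does not say whether ALT and AST are among the limited endpoints repeated as randomised.

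Second, both documents plan descriptive safety analysis without testing, so nothing in the plan turns on whether an interval excludes zero. This stands against using the rates in step 4 as error rates of the plan; they are general properties of one-sample intervals under assumed shared changes. It does not stand against the remedy: a difference with an interval and no p-value is still descriptive, and the SAP already commits to intervals.

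Third, a reader might infer that intervals on the most extreme change are uninformative by construction. Step 5 shows that this holds under one of two readings, and the SAP adopts neither.

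Fourth, multiplicity. About 22 continuous parameters × 5 visits × 2 doses gives 220 differences, of which about 11 (5%) would exclude zero by chance. That is true, but the present plan already yields 22 × 5 × 3 arms = 330 within-arm intervals for change alone.

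Fifth, the pooled placebo group is partly non-concurrent, because the 25 mg cohort finishes treatment before 50 mg enrolment starts (Protocol 7.1). This stands as a caveat. The efficacy analyses already accept it.

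Finally, the SAP does not use the term within-arm. That is the natural reading of SAP 8.5 with 7.5, but it is a reading.

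**Conclusion.** The point holds for laboratory parameters that are not also analysed as efficacy. For these, SAP 8.5.2 plans intervals on change within each arm and no estimate against placebo, although the comparison with placebo is a primary objective and several of these parameters feed the protocol's liver-injury rules. It does not hold for ALT, AST, lipids, the metabolic panel or blood pressure.

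This is a gap in reporting, not a flaw in design or data collection. The missing interval would have a half-width of about 0.52 SD at 30 v 30, against 0.37 SD for the one planned, so the planned tables also show less uncertainty than the comparative question carries. The conclusion rests on reading the intervals as within-arm. The widths assume equal SDs across arms and complete data.

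**What to change.** In SAP 8.5.2, replace the within-arm intervals, or supplement them, with wording such as: *for each continuous laboratory parameter and visit, the difference in mean change from baseline between each randomised TVB-2640 dose group and pooled placebo, adjusted for the baseline value, will be presented with its 95% confidence interval, descriptively and without p-values.* Add a cross-reference to the ALT/AST model in SAP 8.3.2, so that the primary safety objective can be traced to its analysis. Define the direction of the most extreme change for each parameter; if an interval is shown for it, give it only as a difference from placebo.

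The cost is a simple model per parameter and visit, extra columns in the laboratory tables, and no new data. The tables should note that the intervals are unadjusted for multiplicity and that the pooled placebo group is partly non-concurrent. The intervals will be wider than those now planned.
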